**Other Adverse Events Observed in HIV-seropositive Patients**

In addition to controlled clinical trials, THALOMID has been used in uncontrolled studies in 145 patients. Less frequent adverse events that have been reported in these HIV-seropositive patients treated with THALOMID were grouped into a smaller number of standardized categories using modified COSTART dictionary/terminology and these categories are used in the listing below. Adverse events that have already been included in the tables and narrative above, or that are too general to be informative are not listed.

**Body as a Whole:** Ascites, AIDS, allergic reaction, cellulitis, chest pain, chills and fever, cyst, decreased CD4 count, facial edema, flu syndrome, hernia, thyroid hormone level altered, moniliasis, photosensitivity reaction, sarcoma, sepsis, viral infection.

**Cardiovascular System:** Angina pectoris, arrhythmia, atrial fibrillation, bradycardia, cerebral ischemia, cerebrovascular accident, congestive heart failure, deep thrombophlebitis, heart arrest, heart failure, hypertension, hypotension, murmur, myocardial infarct, palpitation, pericarditis, peripheral vascular disorder, postural hypotension, syncope, tachycardia, thrombophlebitis, thrombosis.

**Digestive System:** Cholangitis, cholestatic jaundice, colitis, dyspepsia, dysphagia, esophagitis, gastroenteritis, gastrointestinal disorder, gastrointestinal hemorrhage, gum disorder, hepatitis, pancreatitis, parotid gland enlargement, periodontitis, stomatitis, tongue discoloration, tooth disorder.

**Hemic and Lymphatic:** Aplastic anemia, macrocytic anemia, megaloblastic anemia, microcytic anemia.

**Metabolic and Endocrine:** Avitaminosis, bilirubinemia, dehydration, hypercholesterolemia, hypoglycemia, increased alkaline phosphatase, increased lipase, increased serum creatinine, peripheral edema.

**Muscular Skeletal:** Myalgia, myasthenia.

**Nervous System:** Abnormal gait, ataxia, decreased libido, decreased reflexes, dementia, dysesthesia, dyskinesia, emotional lability, hostility, hypalgesia, hyperkinesia, incoordination, meningitis, neurologic disorder, tremor, vertigo.

**Respiratory System:** Apnea, bronchitis, lung disorder, lung edema, pneumonia (including *Pneumocystis carinii* pneumonia), rhinitis.

**Skin and Appendages:** Angioedema, benign skin neoplasm, eczema, herpes simplex, incomplete Stevens-Johnson syndrome, nail disorder, pruritus, psoriasis, skin discoloration, skin disorder.

**Special Senses:** Conjunctivitis, eye disorder, lacrimation disorder, retinitis, taste perversion.

#### *Postmarketing Experience*

The following adverse reactions have been identified during post approval use of THALOMID. Because these reactions are reported voluntarily from a population of uncertain size, it is not always possible to reliably estimate their frequency or establish a causal relationship to drug exposure.

**Cardiovascular System:** Cardiac arrhythmias including atrial fibrillation, bradycardia, tachycardia, sick sinus syndrome, EKG abnormalities, myocardial infarction.

**Digestive System:** Intestinal perforation, gastrointestinal perforations, intestinal obstruction.

**Metabolic and Endocrine:** Electrolyte imbalance including hypercalcemia or hypocalcemia, hyperkalemia and hypokalemia, hyponatremia, hypothyroidism, increased alkaline phosphatase, tumor lysis syndrome.

**Nervous System:** Changes in mental status or mood including depression and suicide attempts, disturbances in consciousness including lethargy, syncope, loss of consciousness or stupor, seizures including grand mal convulsions and status epilepticus, Parkinson's disease, stroke.

**Skin and Appendages:** Erythema multiforme, toxic epidermal necrolysis.

**Hemic and Lymphatic:** Decreased white blood cell counts including neutropenia and febrile neutropenia, changes in prothrombin time, pancytopenia.

**Respiratory System:** Pleural effusion.

**Reproductive System and Breast Disorders:** amenorrhea, sexual dysfunction.

**Immune System Disorders:** Hypersensitivity, angioedema/urticaria.

Ear and Labyrinthine Disorders: Hearing impairment/deafness.

Renal and Urinary Disorders: Renal failure.

*Other Adverse Events in the Published Literature or Reported from Other Sources*

The following additional events have been identified either in the published literature or from spontaneous reports from other sources: acute renal failure, amenorrhea, aphthous stomatitis, bile duct obstruction, carpal tunnel, chronic myelogenous leukemia, diplopia, dysesthesia, dyspnea, enuresis, erythema nodosum, erythroleukemia, foot drop, galactorrhea, gynecomastia, hangover effect, hypomagnesemia, hypothyroidism, lymphedema, lymphopenia, metrorrhagia, migraine, myxedema, nodular sclerosing Hodgkin's disease, nystagmus, oliguria, pancytopenia, petechiae, purpura, Raynaud's syndrome, stomach ulcer, suicide attempt, interstitial lung disease and severe infections (e.g., fatal sepsis including septic shock).

#### 9.1.5 Composition and Dosage Forms

| Dosage forms and composition |              |   |   |
|-------------------------------------|--------------|---|---|
| Strength                            | Color        | Imprint                                       | Non-medicinal ingredients   |
| 50 mg                               | White opaque | Do Not Get Pregnant woman logo CELGENE 50 mg  | pregelatinized starch and magnesium stearate; capsule shell contains gelatin, titanium dioxide and black ink*                                       |
| 100 mg                              | Tan opaque   | Do Not Get Pregnant woman logo CELGENE 100 mg | pregelatinized starch and magnesium stearate; capsule shell contains gelatin, black iron oxide, yellow iron oxide, titanium dioxide, and black ink* |
| 200 mg                              | Blue opaque  | Do Not Get Pregnant woman logo CELGENE 200 mg | pregelatinized starch and magnesium stearate; capsule shell contains gelatin, FD&C blue #2, titanium dioxide, and white ink                         |

\* The 50 mg and 100 mg capsule shells have black ink which contains shellac and black iron oxide.

[figure not shown]
*Drug Substance:*

Proper name: thalidomide

Chemical name:  $\alpha$ -(N-phthalimido) glutarimide

Molecular formula and molecular mass:  $C_{13}H_{10}N_2O_4$ , 258.2 g

Structural formula:

**Physicochemical properties:** Thalidomide is an off-white to white, odorless, crystalline powder that is soluble at 25°C in dimethyl sulfoxide and sparingly soluble in water and ethanol. The glutarimide moiety contains a single asymmetric center and, therefore, may exist in either of two optically active forms designated S-(-) or R-(+). Thalidomide used in THALOMID® contains an equal mixture of the S-(-) and R-(+) forms and, therefore, has a net optical rotation of zero.

#### 9.1.6 Storage Recommendations

Store at 15-30° C. Keep out of the reach of children.

#### 9.1.7 Dispensation and Accountability

THALOMID® is only available through a controlled distribution program called THALOMID® REMSTM. Under this program, only enrolled prescribers and program-certified pharmacists are able to prescribe and dispense the product. In addition, THALOMID® can only be dispensed to patients who are registered and meet all the conditions of the REMSTM program.

For more information, call the manufacturer (Celgene Customer Care Center) toll-free number at [name] or log on to the [www.CelgeneRiskManagement.com](http://www.CelgeneRiskManagement.com) website.

#### 9.1.8 SPECIAL HANDLING INSTRUCTIONS

Currently, no published data are available regarding the cutaneous absorption of thalidomide.

Most health care institutions recommend that latex gloves be worn while handling chemotherapeutic agents. Health care providers may consider wearing gloves when directly handling THALOMID® (thalidomide capsules), along with standard hand washing. Females who could become pregnant, or who plan to become pregnant can handle THALOMID® capsules if they are using latex gloves.

Rerecycling of THALOMID® must only be done on exceptional circumstances. This should only be done by pharmacists.

## 10.0 TREATMENT/ DOSE MODIFICATIONS

### 10.1 Unacceptable Toxicity

Development of grade 3-4 peripheral neuropathy that is considered to be related (possibly, probably or definitely) and unacceptable (because of severity and/or irreversibility) will require THALIDOMIDE discontinuation.

### 10.2 Dose Modification Guidelines for Thalidomide (THALOMID®)

Thalidomide (THALOMID®) will be administered as per standard of care guidelines and in compliance with REMS™ program requirements.

## 11.0 STUDY/TREATMENT DISCONTINUATION

Study participation/Treatment may be discontinued for any of the following reasons:

- The patient withdraws consent from the study
- (**Group A**): The patient experiences an adverse event that in the opinion of the Investigator makes continued study treatment an unacceptable risk
- (**Group A**): The patient experiences unacceptable toxicity as described in Section 10.1
- The patient is significantly noncompliant with the requirements of the protocol

Should discontinuation of study therapy occur (for Group A patients), all efforts should be made to execute/ report End-of-Treatment and/or Follow-up Evaluations as completely as possible *and* to determine/ document the reason for discontinuation (unless the patient withdraws consent).

If a patient wishes to withdraw consent from the study, the PI must be notified. The information regarding withdrawal (i.e. subject identifiers and date of withdrawal) should be documented in the subject's record and updated within any other research database(s).

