## PROTOCOL SYNOPSIS

|                                    |   |
|------------------------------------|---|
| Protocol Title              | Long-term Follow-Up and/or Continued Thalidomide (THALOMID®) Maintenance Therapy for Patients Enrolled on Clinical Trial 20030165   |
| Targeted Patient Population | Patients enrolled on Clinical Trial 20030165.   |
| Study Design                | 
The study is designed to provide long-term follow-up and/or to offer continued maintenance thalidomide (THALOMID®) therapy to those patients enrolled in 20030165.
 
Group A: Patients who achieved CR in 20030165 and continue to receive maintenance Thalidomide.
 
Group B: Patients who achieved CR in 20030165, but are not receiving maintenance Thalidomide.
 
Group C: All other patients enrolled in 20030165 who expired or experienced disease progression.
 |
| Treatment Schema            | Thalidomide (THALOMID®) will be administered as per standard of care guidelines to Group A; in compliance with REMS™ program requirements.  |
| Study Duration              | 
Patients in Group A, B and C will be followed until withdrawal of consent, or death.
 
Note: All other patients in Group C who expired on 20030165 will also be included in all analyses.
  |
| Follow-up Required          | All patients will be followed annually by telephone or in-person visit(s), until death or withdrawal.   |
| Objectives                  | 
Primary Objective: To provide long-term follow-up and/or offer continued maintenance thalidomide (THALOMID®) to patients enrolled in 20030165 .
 
Secondary Objective: To continue to evaluate objectives specified for 20030165 (please refer to 20030165 for details).
  |
| Expected Number of Patients | 
Group A: 2
 
Group B: 12
 
Group C: 8
   |
| Expected Number of Centers  | 1-Sylvester Comprehensive Cancer Center (SCCC)
Note: SCCC is inclusive of the constituent satellite sites.  |

|  |  |
|--|--|
| Expected Duration of the Protocol | At least 5 years.  |
| Inclusion Criteria                | 

1. Enrolled on the 20030165 clinical trial.

2. Ability to understand and willingness to sign a written informed consent document.

  |

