### 8.5 Duration of Treatment

Group A: Patients will continue with thalidomide (THALOMID®) as per standard of care guidelines, until progression of disease, discontinuation due to toxicity, death or study withdrawal. Patients who discontinue thalidomide for any reason other than death, or withdrawal of consent will continue to be followed as per Section 8.6.

See Section 12.0 for evaluations.

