## 12.6 Follow-up Evaluations for All Patients

The following evaluation should be performed at least annually, until death or withdrawal of consent as described for:

- Survival: contact by telephone or in-person visit; Methods used for attempted contact must also be documented properly.

(For Group A, contact should occur after end of treatment visit; for Group B, contact should occur prior to or after disease progression; survival contact for patients in Group C should continue until death or withdrawal of consent.)

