## 13.0 MEASUREMENT OF EFFECT

For the purposes of this study, patients should be evaluated for response every as per standard of care until documented disease progression or study withdrawal (for reasons including toxicity and/or death).

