### 13.5 Progression-Free Survival (PFS)

Patients will be followed at a minimum of annual intervals (every 12 months,  $\pm 30$  days) or as clinically indicated and at the discretion of the Investigator to document the progression-free interval.

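### Section 13.0 treats toxicity as a study withdrawal that ends response evaluation, while Section 8.5 keeps a Group A patient who stops thalidomide for toxicity in follow-up; read literally, PFS could be censored at the treatment stop

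*Protocol*

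**What the plan says.** **Toxicity.** Section 13.0 continues response evaluation "until documented disease progression or study withdrawal (for reasons including toxicity and/or death". Section 8.5 lists toxicity among the reasons for stopping thalidomide and then says: "Patients who discontinue thalidomide for any reason other than death, or withdrawal of consent will continue to be followed as per Section 8.6". Section 8.6 sets annual follow-up and sends the reader to Section 12 for its content.

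**Assessments after treatment.** Section 12.2, which covers Group A on treatment, holds the annual physical exam, blood count, metabolic panel and LDH. Section 12.5 repeats that set once, about 30 days after the last dose. Section 12.6 then names one item: "Survival: contact by telephone or in-person visit". The 12.7 calendar lists the 12-monthly exam and labs without the Group A footnote, and its follow-up column shows survival only. Section 13.5 says of PFS: "Patients will be followed at a minimum of annual intervals".

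**Endpoint.** Under 3.1, PFS runs from enrollment in 20030165 to progression or death from any cause. Patients without progression are censored at their last evaluable disease assessment.

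**Noncompliance.** Section 11 gives one list of reasons for which participation or treatment may end. The adverse-event and toxicity items are tagged Group A. "The patient is significantly noncompliant with the requirements of the protocol" carries no tag. The Synopsis Study Duration row says: "Patients in Group A, B and C will be followed until withdrawal of consent, or death".

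**The concern.** Stopping a drug and leaving a study are different events, and a follow-up protocol with PFS as its primary endpoint has to keep them apart. Section 13.0 merges them for toxicity. Because 3.1 sets the censoring date from the last assessment, an instruction that ends assessments also fixes the censoring date. A patient who stops thalidomide for neuropathy, which Section 10.1 can require, would be censored for a reason tied to treatment, and a progression after that date might never be looked for. An analysis plan cannot recover assessments that were not made, so the protocol has to settle this.

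**Working it through.** The protocol gives no power, event or dropout figure to reproduce. The check is a comparison of text, followed by a bound on size.

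**Text comparison**

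1. *13.0 against 8.5.* Same patient (Group A, stops for toxicity), same question (is this person still on study?). Section 13.0 says withdrawn; 8.5 says still followed. Both cannot be applied.
2. *What follow-up then contains.* The chain is 8.5 to 8.6 to Section 12. For a Group A patient off treatment, 12.5 gives one exam and lab set and 12.6 gives survival contact. Nothing there says that the annual exam and labs continue.
3. *Text pointing the other way.* The 12.7 calendar does not limit the annual exam and labs to patients on treatment, and 13.5 makes no off-treatment exception. Continued assessment is implied but not stated.
4. *Consequence under 3.1.* If a site follows 13.0 literally, the last assessment is likely to be the 12.5 visit, and a living, progression-free patient is censored there.
5. *What is still captured.* Survival contact continues under 12.6, and death without progression is a PFS event. Appendix B asks for a form within 4 weeks of learning of a progression. The exposed case is a progression that nobody looks for in a patient still alive at analysis.

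**Size**

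Inputs from the Synopsis: Group A 2, Group B 12, Group C 8. Groups A and B: 2 + 12 = 14. All: 14 + 8 = 22.

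- Exposed share of Groups A and B: 2/14 = 14.3%.
- Exposed share of all patients: 2/22 = 9.1%.

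Assumptions for a bound: all 8 Group C patients had a PFS event before roll-over; the 14 others were event-free then; everyone else is fully followed; each affected patient is alive at analysis and is censored before any later event; any later progression in them goes unrecorded. Let k be the later events among the patients still assessed and j the unrecorded progressions.

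- One patient censored: Kaplan-Meier PFS = (14/22)(13 − k)/13; with full follow-up = (14 − k − j)/22; difference = (j − k/13)/22.
- Both censored: Kaplan-Meier PFS = (14/22)(12 − k)/12; with full follow-up = (14 − k − j)/22; difference = (j − k/6)/22.

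With k = 3, which is assumed because the protocol gives no rate:

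| Censored early | Kaplan-Meier | Full follow-up | Difference (points) |
|---|---|---|---|
| One, j = 0 | 49.0% | 50.0% | −1.0 |
| One, j = 1 | 49.0% | 45.5% | +3.5 |
| Both, j = 0 | 47.7% | 50.0% | −2.3 |
| Both, j = 2 | 47.7% | 40.9% | +6.8 |

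Over every possible k, the difference cannot exceed 1/22 = 4.5 points either way for one patient, or 2/22 = 9.1 points for both. These are outer limits, not forecasts. If an affected patient dies, the death is recorded as an event, so the missed-progression rows no longer describe that patient.

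**The case against.** The best defence is that the operative text already handles toxicity correctly. Section 10.1 speaks only of stopping the drug, Section 11 tags its toxicity items to Group A, and it adds: "Should discontinuation of study therapy occur (for Group A patients), all efforts should be made to execute/ report End-of-Treatment and/or Follow-up Evaluations". Section 8.5 is explicit. Against these stands one parenthesis in a sentence of 13.0 that is visibly misdrafted. This lowers the chance that a site would go wrong. It does not reconcile 13.0 with 8.5, and the follow-up evaluations that Section 11 asks for come down to survival contact in 12.6.

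Three stronger readings are tempting and are not supported:

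- *That 13.0 also contradicts 12.6, 13.5 and the Synopsis.* Section 12.6 covers survival contact, which can continue after response evaluation ends. The Synopsis allows follow-up by telephone. Section 13.5 has no stopping rule, so any conflict there is by implication only.
- *That the noncompliance reason in Section 11 flatly contradicts the follow-up rules.* Section 11 is permissive. The Synopsis Follow-up Required row ends follow-up at death or an unqualified withdrawal, and 8.6 refers to withdrawal from the study. Both leave room for removal under Section 11. They are looser than the Study Duration row and 12.6, which makes this an alignment matter. A patient who misses annual exams has little new PFS information anyway, and the documents give no rate from which to estimate an effect.
- *That PFS would be materially biased.* The largest figures need both Group A patients to stop for toxicity, 13.0 to be followed over 8.5, both to progress, and both to be alive at analysis with the progression unrecorded.

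**Conclusion.** The contradiction between 13.0 and 8.5 is real. The layout of 12.2 and 12.6 compounds it by not saying that annual assessment continues after thalidomide stops. The consequence is conditional: if a site applies 13.0 literally, a progression-free Group A patient who stops for toxicity could have PFS censored near the treatment stop, and a later progression could be missed while a death would not be.

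At most the 2 expected Group A patients are exposed. Neither the direction nor the size of any distortion can be known in advance, and the figures above rest on the stated assumptions. Section 15 plans no formal analysis and foresees integration with the 20030165 results only if the principal investigator judges it necessary. Severity is therefore minor. The change is still worth making because it is nearly free and removes a route to toxicity-related censoring of the primary endpoint.

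**What to change.** 1. In 13.0, delete toxicity as a reason for study withdrawal.
2. In 12.2 and 12.6, state that the annual exam and labs continue until progression, death or withdrawal of consent for Group A patients who stop thalidomide without progression.
3. As a secondary alignment, state in Section 11 that noncompliance may stop thalidomide but does not end survival contact, and change the wording of 8.6 to withdrawal of consent, matching 12.6 and the Synopsis Study Duration row.

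The cost is a few sentences, plus one exam and lab set a year, already implied by 12.7 and 13.5, for at most 2 expected patients.

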## 12.0 SCHEDULE OF CLINICAL & LABORATORY EVALUATIONS

### 12.1 Pre-Treatment Evaluations (Screening)

Prior to performing any study-specific procedures or evaluations, written informed consent and authorization for the use of protected health information (HIPAA) must be obtained in accordance with all applicable policies, regulations and laws.

### 12.2 Evaluations on Treatment for Group A

The following evaluations should be performed as described. Additional tests are at the discretion of the Investigator.

#### 12.2.1 Monthly (every 4 weeks, ±5 days)

- **Additional for Women of Childbearing Potential (WoCBP) receiving thalidomide maintenance therapy (Group A):** Serum pregnancy test: (beta-HCG)
- Adverse Events (AEs): Monitoring and collection of Adverse Events (AEs) should occur throughout the study for patients in Group A.

#### 12.2.2 Annually (every 12 months, ±30 days)

- Physical exam (PE)
- Complete Blood Count (CBC), including
  - Differential (diff) and
  - Platelet count (PLT)
- Comprehensive Metabolic Panel (CMP)
- Lactate dehydrogenase (LDH)

#### 12.3 Evaluations on Study for Group B

The following evaluations should be performed as described. Additional tests are at the discretion of the Investigator.

#### 12.3.1 Annually (every 12 months, ±30 days)

- Physical exam (PE)
- Complete Blood Count (CBC)
  - Differential (diff) and
  - Platelet count (PLT)
- Comprehensive Metabolic Panel (CMP)
- Lactate dehydrogenase (LDH)

#### 12.4 Evaluations on Study for Group C

The following evaluation(s) should be performed as described until death or withdrawal of consent as described. Additional tests are at the discretion of the Investigator.

#### 12.4.1 Annually (every 12 months, ±30 days)

- Survival: contact by telephone or in-person visit; Methods used for attempted contact must also be documented properly.

#### 12.5 Off-Treatment Evaluations (End of Treatment or EOT) for Group A

The following assessments should be performed at the EOT visit and should occur 30-days (± 5 days) after the last dose of thalidomide.

- Physical exam (PE)
- Complete Blood Count (CBC), including
  - Differential (diff) and
  - Platelet count (PLT)

- Comprehensive Metabolic Panel (CMP)
- Lactate dehydrogenase (LDH)
- **(Additional for WoCBP)** Serum pregnancy test: (beta-HCG)

